## 4 STUDY DESIGN

### 4.1 OVERALL DESIGN

Study Design:

This study is an unblinded, uncontrolled, unrandomized, 1-arm clinical trial.

Hypotheses:

We hypothesize that easy to use, accurate, exogenous cueing in response to FOG events will decrease duration these events.

Randomization:

N/A

Study Intervention:

Participants will be provided a haptic module and insole device to use within their home and community for 5 weeks. Additional details of the intervention are discussed in **Section 6.1**.

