## 6 STUDY INTERVENTION(S) OR EXPERIMENTAL MANIPULATION(S)

### 6.1 STUDY INTERVENTION(S) OR EXPERIMENTAL MANIPULATION(S) ADMINISTRATION

#### 6.1.1 STUDY INTERVENTION OR EXPERIMENTAL MANIPULATION DESCRIPTION

The study intervention for all participants is the use of the haptic module and insole device within their home and community for 5 weeks. Participants will be asked to wear the devices as much as possible during the 5-week period. For example, whenever they don their shoes to walk around within their home or the community, they will also wear the devices. Participants will receive the system with cueing disabled. Cueing will be enabled at the end of week 1 and disabled at the end of week 4 automatically via the cellular base station provided to participants. If any issues occur with the remote enabling and disabling of the cueing devices, participants will be instructed to stop wearing the devices during weeks 1 & 5.

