#### 6.1.2 ADMINISTRATION AND/OR DOSING

The main purpose of this study is to establish the robustness and efficacy of the haptic module and insole device through long-term, continuous use while subjects proceed with their activities of daily living at home and in the community. Data will be collected in three parts. Part 1 will collect data for 7 days with the cueing intervention turned off to establish a baseline. Part 2 will collect data over 21 days with the cueing intervention turned on. Part 3 will examine the wash-out effects of cueing by collecting for an additional 7 days with the cueing intervention turned off. Throughout this trial, daily dairies of FOG episodes, user impressions, and adverse events will be collected. Data from the insole will automatically (no participant interaction for the duration of the study) be downloaded by the charging mat's nRF52840

BLE radio/processor and stored to a secure digital card. Participants will be contacted weekly by the research coordinator to discuss use of the device and compliance with protocol.

The sensing device consists of two parts for each leg: the Haptic Module and the Insole (Figure 1). The Haptic Module wraps around the lower leg (Figure 2) of the user and contains electronics for wireless communication, a microprocessor, and four vibrating motors that provide gentle tactile sensory cues to the front, back, medial, and lateral surfaces of the user's leg when a FOG event is detected. The Haptic Module has a power button, two status LEDs, and a reset button. Power is supplied by a rechargeable internal battery.

The Insole is a pressure-sensitive insert that fits in a regular shoe with a battery and electronics for sampling pressure measurements. The electronics are housed in a sealed plastic case that securely clips to the outside of the wearer's shoe (Figure 2). The insole has a single status light and no buttons. Users recharge the insole and haptics module via USB connectors.

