#### 9.4.2 ANALYSIS OF THE PRIMARY ENDPOINT(S)

The primary outcome measures from this experiment will be the duration of FOG episodes detected by the insole device. A linear mixed effects model (LME, implemented in R) with within-subject factors of intervention (cueing vs. non-cueing) and time (pre vs. post intervention) will be used to test the primary hypothesis. Interaction effects will be tested using Tukey's Honestly Significant (HSD) test. The threshold for significance will be set at the  $p < 0.05$  level. Secondary variables such as the incidence of FOG episodes will be assessed using a Chi-squared analysis.

---

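### The primary model crosses cueing with pre/post, but the off-on-off design fills only three of the four cells: the planned interaction cannot be estimated, and the plan does not fix which contrast is the cueing effect

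*Combined protocol and SAP*

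**What the plan says.** Section 9.4.2 names insole-detected episode duration as the primary outcome. For the linear mixed model it states that "within-subject factors of intervention (cueing vs. non-cueing) and time (pre vs. post intervention) will be used to test the primary hypothesis". It continues: "Interaction effects will be tested using Tukey's Honestly Significant (HSD) test".

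The data come from three phases in a fixed order (section 6.1.2):

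- The first phase, week 1, is the reference: "Part 1 will collect data for 7 days with the cueing intervention turned off to establish a baseline".
- The second phase, weeks 2-4, is 21 days of recording while cueing is active.
- The third phase, week 5, has its own purpose: "Part 3 will examine the wash-out effects of cueing by collecting for an additional 7 days with the cueing intervention turned off".

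Section 6.1.1 confirms the switching: "Cueing will be enabled at the end of week 1 and disabled at the end of week 4 automatically". Section 4.1 confirms that no other group could supply a missing combination: "This study is an unblinded, uncontrolled, unrandomized, 1-arm clinical trial".

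Section 9.2 sizes the trial for a repeated-measures ANOVA with two conditions, sham and intervention. It gives an effect size of 0.29, power of 0.85, p < 0.05, 29 evaluable and 36 recruited. No sham period is described elsewhere. Nothing in the document says whether the cueing weeks count as pre or post, or which coefficient or contrast tests the primary hypothesis.

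**The concern.** A two-by-two within-subject model needs data in all four combinations of its factors. Here cueing is on in one block of weeks only, so it is observed at one level of time at most. An interaction asks whether the cueing effect differs between pre and post, and no participant supplies the data to answer that. Tukey's HSD compares pairs of means. It is not a test of interaction and cannot fill an empty cell.

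The second issue is which comparison the cueing term makes. Section 6.1.2 calls week 1 the baseline, so cueing against week 1 is the natural test of the hypothesis in section 9.1. The two factors in section 9.4.2 do not secure that comparison. The coding would be settled at analysis, possibly after the data have been seen, and if the cueing effect partly persists in week 5 the choice changes both the estimate and the power of the trial's one primary test.

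**Working it through.** **1. The plan's own sample size.** Section 9.2 gives 0.29, 0.85 and 0.05. It does not give the type of effect size or the within-person correlation ρ. Assume Cohen's f, ρ = 0.5 and m = 2 conditions. Then λ = f² × N × m / (1 − ρ) = 0.0841 × 29 × 2 / 0.5 = 9.76 on 1 and 28 df, and power is 0.854. N = 28 gives 0.841, so 29 reproduces. Other correlations give N = 56 (ρ = 0), 40 (0.3) and 19 (0.7). Reading 0.29 as a standardised paired difference gives 109. For attrition, 29 / 0.8 = 36.25, close to the stated 36.

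The equivalent standardised paired difference is dz = 0.29 × √(2 / 0.5) = 0.58.

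**2. Which cells exist.**

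| Phase | Cueing | Time |
|---|---|---|
| Week 1 | off | pre |
| Weeks 2-4 | on | not stated |
| Week 5 | off | post |

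Three phase means cannot identify four coefficients. With columns for intercept, cueing, time and their product, the matrix has rank 3 of 4 whether weeks 2-4 are coded pre or post. If time means only week 1 against week 5, the cueing weeks have no time level and the rank is 2.

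**3. What the additive model estimates.** Without the product, the matrix has full rank, 3 of 3. Inverting it gives:

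| Coding of weeks 2-4 | Cueing coefficient | Time coefficient |
|---|---|---|
| post | weeks 2-4 minus week 5 | week 5 minus week 1 |
| pre | weeks 2-4 minus week 1 | week 5 minus week 1 |
| time dropped | weeks 2-4 minus pooled off weeks | none |

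**4. When the choice matters.** Let c be the share of the effect still present in week 5 (no value in the documents). Take one mean per participant per phase, with equal variances and equal correlations; the pooled contrast weights the two off weeks equally.

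- Against week 1: dz = 0.58.
- Against week 5: dz = 0.58 × (1 − c).
- Against pooled off weeks: dz = 0.58 × (1 − c/2) / √0.75. The divisor appears because averaging two off weeks cuts the variance of the difference from 2σ²(1 − ρ) to 1.5σ²(1 − ρ).

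Two-sided paired t test, n = 29, ρ = 0.5:

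| c | Week 1 | Week 5 | Pooled off |
|---|---|---|---|
| 0 | 85% | 85% | 94% |
| 25% | 85% | 62% | 86% |
| 50% | 85% | 33% | 74% |
| 75% | 85% | 12% | 59% |

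At c = 50% over the unstated correlation, with dz = 0.29 × √(2 / (1 − ρ)) in place of 0.58:

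| ρ | Week 1 | Week 5 | Pooled off |
|---|---|---|---|
| 0 | 57% | 19% | 46% |
| 0.3 | 72% | 25% | 60% |
| 0.5 | 85% | 33% | 74% |
| 0.7 | 97% | 49% | 92% |

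**5. Power after the repair.** With a three-level phase factor, the contrast of weeks 2-4 with week 1 has noncentrality 0.58 × √29 = 3.12 on 2 × 28 = 56 df, and power is 87%. If the same contrast is tested only as one of three Tukey-adjusted pairs (critical value 2.41), power is 76%. Reaching 85% would then take 36 evaluable, or 36 / 0.8 = 45 recruited.

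**The case against.** The strongest reply is that the plan is loosely worded rather than unworkable. Several parts of it stand.

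- A reader might infer that the model yields the wrong contrast. The documents do not support that. If weeks 2-4 are coded pre, so that post means after cueing has ended, the cueing coefficient is exactly cueing minus baseline. Calling the intervention weeks pre-intervention is strained, but the text does not exclude it. The defect is an unfixed contrast.
- A reader might infer that the wash-out question is lost. It is not: the additive model estimates week 5 minus week 1 under either coding.
- A reader might infer that the model will fail to run. That is not shown. Section 9.4.2 names R but no package, and software may simply drop the aliased interaction column.
- A reader might infer that the protocol predicts carry-over. Section 6.1.2 says only that wash-out will be examined. The cue is given when an event is detected, so carry-over could be small. With none, all three contrasts estimate the same effect and the pooled one has the most power.
- The pooled contrast can be a sensible choice, because weeks 1 and 5 lie symmetrically around weeks 2-4 and a linear drift would cancel. The plan does not say that this is intended.
- The Tukey sentence can be read as pairwise comparison of the three observed cells. Cueing against baseline would then be available, but as one of three adjusted pairs with nothing naming it as primary.

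None of this makes the stated interaction estimable or says which contrast decides the trial.

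**Conclusion.** The point holds in two parts. First, the interaction planned in section 9.4.2 cannot be estimated from the off-on-off design. This needs no assumption: three cells, four coefficients, rank 3. It is an analysis that the design cannot support, not just a missing detail. Second, the plan does not fix the cueing effect as cueing against baseline; three contrasts are open, depending on how time is coded or whether it is kept.

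The cost of the second part is conditional. At 50% carry-over, with f = 0.29 and ρ = 0.5, power is 85%, 33% or 74% according to the contrast. Over ρ from 0 to 0.7 the last two run from 19% to 49% and from 46% to 92%. The effect-size type, the correlation and the carry-over share are assumptions made here. With no carry-over the choice does not change the expected estimate.

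**What to change.** In section 9.4.2:

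- Replace both factors with one three-level phase factor (week 1 off, weeks 2-4 on, week 5 off).
- Name weeks 2-4 minus week 1 as the single primary contrast, two-sided 0.05, with no Tukey adjustment.
- Report week 5 minus week 1 (wash-out) and weeks 2-4 minus week 5 (reversal) as secondary contrasts with confidence intervals.
- Delete the sentence on interaction and Tukey's HSD.

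In section 9.2, reconcile the sham-versus-intervention description with the three phases, and state the type of effect size and the correlation behind 29.

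The cost is a few lines of text before database lock and no new data. Under f = 0.29 and ρ = 0.5 the named contrast has 87% power at 29, so 29 evaluable and 36 recruited can stand. The change makes the contrast definite, but it remains a before-after comparison in a single arm.

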#### **3. Study Intervention**

- Participants will wear the haptic module and insole device as often as possible for 5 weeks within their home and the community. They will also complete a daily FOG diary.
- Research staff will:
  - Call participants weekly to check in regarding any issues with the device and complete the AE/SAE reporting form in REDCap (approximately 15-30 minutes).

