# 8 STUDY ASSESSMENTS AND PROCEDURES

## 8.1 ENDPOINT AND OTHER NON-SAFETY ASSESSMENTS

**Demographics:** Demographic information will be collected, including gender, age, race, ethnicity, height, weight, marital status, and employment status.

**Protected health information collected:** Name, medical record number, birth date, phone number, address, email address, and medical history, including date of PD diagnosis.

**New Freezing of Gait Questionnaire (NFOG-Q):** The NFOG-Q is a self-report questionnaire with 9 items that measure FOG.

**Characterizing Freezing of Gait Questionnaire (C-FOGQ):** The C-FOGQ is a self-report questionnaire that provides insights into the triggers of freezing.

**Falls Questionnaire:** The falls questionnaire is a 4-item self-report survey including questions about any recent falls. The questionnaire was developed by the [name] at the University of Minnesota.

**FOG Diary:** Participants will be provided paper diaries to keep track of their FOG events and will be asked to report the information during the weekly phone call for the 5-week intervention.

**Adherence:** The participant's adherence to using the haptic module and insole device will be measured. Daily use of the device will be recorded during the weekly phone call for the 5-week intervention.

**Structured Interview:** Participants will be asked to complete a structured questionnaire at the post-treatment visit. The interview will include questions about their experience with using the device within their home and community.

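### The chi-squared test named for FOG incidence has no pairing, rate or exposure term, and does not fit a one-arm design with 7-, 21- and 7-day phases and free wear time.

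*Combined protocol and SAP*

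**What the plan says.** Section 9.4.2 first sets out a linear mixed model for episode duration with "within-subject factors of intervention (cueing vs. non-cueing) and time (pre vs. post intervention") and a 0.05 threshold. It then closes with one sentence on everything else: "Secondary variables such as the incidence of FOG episodes will be assessed using a Chi-squared analysis". Nothing further is specified. Sections 9.3 (populations) and 9.4.3 (secondary endpoints) are both marked not applicable.

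The data that this test would receive are described elsewhere:

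- Section 4.1: "This study is an unblinded, uncontrolled, unrandomized, 1-arm clinical trial". Every comparison is therefore within the same people.
- Section 6.1.2 opens with one week at 7 days off and closes with another for wash-out. The phase between them is three times as long: "Part 2 will collect data over 21 days with the cueing intervention turned on".
- Section 1.3, study intervention: "Participants will wear the haptic module and insole device as often as possible for 5 weeks". Exposure is left to the participant.
- Section 8.1: "Daily use of the device will be recorded during the weekly phone call for the 5-week intervention". Use is collected, but no analysis takes it as a denominator.

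**The concern.** A standard chi-squared test assumes independent units and, for event counts, a known split of observation time. Neither is secured here. Cueing-on time is 21/7 = 3 times the baseline and 21/(7 + 7) = 1.5 times all cueing-off time. Worn hours can also differ by person and by phase. In addition, a participant's own freezing rate may move from one phase to the next for reasons unrelated to cueing.

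Incidence matters because episode duration is observed only when an episode is detected. Shorter episodes that became more frequent, or longer ones because brief freezes disappeared, can be told apart only with a sound rate. The error can also work against the device: with raw counts, the longer cueing window makes cueing look as if it increases freezing.

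**Working it through.** **The plan's own figure.** Section 9.2 gives 29 evaluable participants from effect size 0.29, power 0.85 and alpha 0.05 for a two-condition repeated-measures ANOVA. With λ = f²·N·m/(1 − ρ), m = 2 and ρ = 0.5 (ρ is not stated in the plan), λ = 0.0841 × 29 × 2/0.5 = 9.76 on 1 and 28 df. Power is 0.854, so 29 reproduces. For attrition, 29/0.8 = 36.25, against 36 planned. No figure is given for incidence.

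**Inputs.** From the documents: N = 29, alpha 0.05, phases of 7, 21 and 7 days. Assumed, because the documents give none: 1, 5 or 10 episodes per day, the spread of rates between people, the person-by-phase spread (log-SD), and relative wear.

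**Why exposure matters.** Take 5 episodes per day for everyone and no effect. Expected counts are 5 × 14 × 29 = 2,030 off and 5 × 21 × 29 = 3,045 on, total 5,075.

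- Against an equal split: (2,030 − 2,537.5)²/(5,075 × 0.25) = 203, where the critical value is 3.84.
- Corrected for days (off share 14/35 = 0.4), but with wear 10% lower during cueing: on-count 2,740.5, total 4,770.5, expected off 1,908.2. The statistic is 121.8²/(4,770.5 × 0.24) = 13.0.

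**Why person-by-phase variation matters.** With log-SD 0.2 the squared coefficient of variation is e^0.04 − 1 = 0.0408. One person's off-count (mean 70) has variance 70 + 70² × 0.0408 = 270, and the on-count (mean 105) has 105 + 105² × 0.0408 = 555. For the contrast 0.6·off − 0.4·on, chi-squared assumes a variance of 0.36 × 70 + 0.16 × 105 = 42. The actual value is 0.36 × 270 + 0.16 × 555 = 186, or 4.4 times as large.

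**Null simulation, pooled counts.** 4,000 trials per setting, 7 vs 21 and 14 vs 21 days unless noted. Ranges run over the three rates.

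| Setting, no true effect | Lognormal person rates, log-SD 1.0 | Gamma person rates, shape 1 |
|---|---|---|
| Unequal time ignored | about 94-100% | 96-100% |
| Calendar days corrected, person-by-phase log-SD 0.2 | about 23-69% | 14-59% |
| Same, larger log-SD | about 58-87% (0.5) | 35-79% (0.4) |
| Calendar days corrected, wear 10% lower during cueing, no other variation, 14 vs 21 days | about 53-100% | 37-99.7% |
| Exact exposure, stable person rates | about 5% | 4.5-5.8% |
| Paired t on log rate, exact exposure, 14 vs 21 days | about 5% | 3.7-5.4% |

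For 7 vs 21 days the paired test gave 4.4-5.2% at 5 to 10 episodes per day (gamma rates). At 1 per day it gave 7.8-9.1%, because the 0.5 added to sparse counts biases the log rate.

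**Any-episode table.** If incidence means participants with at least one episode, P(any) = 1 − exp(−rate × days) grows with the window. At 0.05 to 0.3 episodes per day, null rejection for 7 vs 21 days is about 45-58%. At a median of 1 per day, about 96% and 99.5% of participants have an episode in 7 and 21 days. Rejection is then about 0-3%, and the table can show almost nothing.

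**The case against.** The strongest reply is that the plan does not define the table, so no single error rate belongs to it. That stands. A reader might infer from the 94-100% figure that the trial is nearly certain to report a false effect on incidence. The documents do not support this: they nowhere say that raw totals will be tested against an equal split.

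A reader might also infer that repeated episodes from the same people invalidate the test by themselves. They do not. With exposure exactly corrected and stable person rates, rejection is near 5%. The harm comes from uncorrected exposure and from person-by-phase variation, and the sizes of both are assumed.

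The direction can even reverse. If each participant had the same chance of any episode in both periods, an unpaired chi-squared on paired data would be conservative: null rejection falls from 0.029 to 0.001 as the latent correlation rises from 0.3 to 0.9. The windows are unequal, however, so this does not rescue an any-episode table.

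Finally, duration is the only endpoint listed in Sections 1.1, 3 and 9.1. Incidence appears only as an example of a secondary variable. That limits the severity. It does not make the named test suitable.

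**Conclusion.** The point holds as a mismatch between a named method and the design. No common reading of the chi-squared serves: pooled counts are exposed to unequal time, uneven wear and person-by-phase variation, and an any-episode table is driven by window length when episodes are rare and close to uninformative when they are common. The sizes above rest on assumed rates and spreads; across the range tried, the pooled-count inflation is large whenever exposure is wrong or rates vary by phase.

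This is something the sponsor should fix, not a flaw in the primary result. A reader might infer that the duration test is also undermined, or that participants with no episodes in a phase vanish from it. The documents do not support either. The mixed model for duration is a separate analysis, it keeps a participant's data from other phases, and N = 29 does not depend on incidence.

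**What to change.** In Section 9.4.2, replace the chi-squared with a within-person count model:

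- Outcome: episodes per participant-phase, negative binomial or overdispersed Poisson.
- Terms: a three-level phase factor (baseline, cueing, wash-out), a random participant effect, and log worn time as offset. Add a participant-by-phase random effect only if counts are modelled per day; with one count per participant-phase it duplicates the dispersion parameter.
- Report: rate ratios with 95% confidence intervals and, descriptively, frozen time per worn hour.
- Worn time: from the insole recordings if they allow it, otherwise from the daily use recorded at the weekly calls (Section 8.1). The documents do not describe a device measure of wear, so state which source is used.
- Participant-phases without wear, which Section 6.1.1 foresees if remote switching fails, contribute no data.

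A paired analysis of log rate per worn hour is an acceptable simple alternative where counts are not sparse. The simulation tested that paired analysis, not the mixed model itself.

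The cost is revised wording and modest programming to derive worn time. No extra visits or participants are needed. The change should be written in before the data are analysed.

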#### 9.4.3 ANALYSIS OF THE SECONDARY ENDPOINT(S)

N/A

---

#### 9.4.4 SAFETY ANALYSES

AE/SAEs will be reported as described in section 8.3 of this document. They will be classified by severity, relationship to study procedures, and expectedness. No other formal safety analyses will be conducted.

---

#### 9.4.5 BASELINE DESCRIPTIVE STATISTICS

Demographic data will be summarized using descriptive statistics (e.g., mean and standard deviation, or frequency and proportion).

---

#### 9.4.6 PLANNED INTERIM ANALYSES

N/A

---

#### 9.4.7 SUB-GROUP ANALYSES

N/A

---

